3. OBJECTIVES

3.1 Purpose:

To determine the feasibility of polymodal spinal cord stimulation therapy in patients with chronic intractable lower back pain with or without leg pain.

3.2 Objective:

To demonstrate that spinal cord stimulation using multiple simultaneous waveforms provides pain relief in patients suffering chronic intractable low back pain with or without leg pain.

3.3 Primary endpoint:

3.3.1 Back pain score reduction relative to baseline pain score (i.e. prior to SCS) at day 5 post-initiation of a particular SCS therapy (conventional or polymodal).

[REDACTED]

[REDACTED]

[REDACTED]

[REDACTED]

[REDACTED]

[REDACTED]

[REDACTED]

[REDACTED]

[REDACTED]

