4. ELIGIBILITY

4.1 Inclusion Criteria:

- 4.1.1** Capable of giving written informed consent to participate in this clinical study based on voluntary agreement after a thorough explanation of the patient's participation is provided to them.
- 4.1.2** Chronic intractable pain of the lower back equal to or greater than pain in lower limbs, and that has been refractory to conservative therapy for ≥ 3 months
- 4.1.3** Must be older than 18 years old.
- 4.1.4** Average back pain intensity of ≥ 5 out of 10 on the numerical pain rating scale (NPRS)
- 4.1.6** Appropriate candidate for spinal cord stimulation trial
- 4.1.7** Subjects must be on a stable dose of pain medication regimen for at least one month.
- 4.1.8** Female patients who are not pregnant and do not plan to become pregnant during the study. Females of child bearing potential must provide a negative pregnancy test and must be using reliable contraception and must continue to use reliable contraception until study completion. Non-childbearing potential is defined as postmenopausal for at least 2 years or surgical sterilization or hysterectomy at least 3 months before study start. Patients who become pregnant or who have a spouse/significant other that becomes pregnant during the course of this study agree to report pregnancy to the study physician/staff
- 4.1.9** Must be able to comply with the requirement of study visits and follow-up and phone visits
- 4.1.10** Have cognitive ability of operate the remote control and follow therapy instructions and directions by investigator

4.2 Exclusion Criteria:

- 4.2.1** Systemic infection
- 4.2.2** Any active implanted device
- 4.2.3** Previous experience with SCS therapy either during a trial or fully implanted
- 4.2.4** Evidence of serious neurological, psychological or psychiatric disorders.

- 4.2.5** Mechanical spinal instability
- 4.2.6** Patients with uncorrected coagulation disorders or who are on anticoagulation therapy and cannot interrupt the therapy
- 4.2.7** Patient who are pregnant, breast-feeding or women of childbearing potential with positive pregnancy tests
- 4.2.8** Human immunodeficiency virus (HIV) infection or a clinically significant infection

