5. DESIGN AND PROCEDURES

5.1 Study Design

This is a prospective, observational cross-over study that will compare conventional SCS and polymodal SCS during two different time windows during an SCS trial period. Up to 25 patients will be included in the study. Figure 1 illustrates a general diagram of the study process. A screening/enrollment visit will assess the eligibility of a potential subject who has already given adequate time to evaluate and discuss the informed consent form. Patients that meet all the inclusion and exclusion criteria and who reaffirm voluntary informed consent to participate in the study will be enrolled. Patients enrolled in the study will visit the clinic to start the SCS trial period which involves the implantation of the stimulation leads and programming of conventional SCS therapy. Conventional SCS therapy will be administered before PM-SCS therapy for 4 ± 1 days. [REDACTED]

[REDACTED]

[REDACTED]

[figure not shown]

Figure 1. Flow diagram of the study process.

After the patient has trialed conventional SCS therapy, there will be a washout period which is expected to last no more than one day. This will allow analgesic effects of the conventional therapy to wear off. The patient will visit the clinic to crossover to PM-SCS therapy and will trial it for 4 ± 1 days. After the trial period is over, the implanted temporary leads will be disconnected from the ENS and removed from the patient and the trial period will end. The trial period during the study will not extend longer than ten days. Table 2 shows a schedule of events.

Table 2. Schedule of Events.

Event\Activity	Enrollment/ Baseline (Day 0)	Start of SCS Trial (0-30 days after enrollment/baseline)	Crossover to Polymodal SCS (3-5 days after start of trial)	End of Study (3-5 days after crossover to PM-SCS)
Informed Consent	X			
Inclusion/Exclusion Criteria	X			
Pregnancy Test^A	X			
General Health and Pain Medications	X			
Pain NPRS	X		X	X
Informed Consent Reaffirmation	X			
Lead Implantation		X		
X-ray Fluoroscopy		X	X	X
Programming of Conventional SCS and start of trial		[X]		
Programming of PM- SCS			[X]	
Stimulation Sensation Assessment				X
Impression of Improvement and Patient Satisfaction				X
Adverse Event Assessment		X	X	X

^A Administered only to subjects of childbearing potential

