5.3 Clinic Visit 1: Enrollment/Baseline Visit

A patient will be enrolled in the study upon signing the ICF, verifying that all inclusion and exclusion criteria are met (using CRF01) and reaffirming voluntary participation, and. Medical history, including pain management, and baseline pain will be collected and recorded in the appropriate CRFs (CRF02, CRF03, and CRF04).

5.4 Clinic Visit 2: Lead Implantation, Conventional SCS Programming and Training Procedure:

Patients will be implanted with commercially available temporary leads as part of the regular SCS trial period and using standard clinical practice. The patient will be placed on a surgical bed in a supine position and may be mildly sedated. The back of the patient will be draped and cleaned using sterile techniques. A properly trained physician will guide and place two percutaneous leads into the epidural space using introducers and steering stylets while under fluoroscopic x-ray guidance. Once the leads are placed above the dorsal aspect of the cord at the proper vertebral level, the introducers and stylets are removed. The exterior portion of the leads will be anchored with sutures or taped firmly to the skin and the proximal ends of the leads connected to an interface cable, which will be plugged into the ENS. The leads and cables will be properly secured to minimize migration of the leads and prevent accidental disconnection. An AP and lateral radiograph of the implanted leads in reference to the vertebral levels will be collected. After the patient has recovered from sedation, programming of conventional SCS therapy will be performed using standard clinical practice.

5.4.1 Conventional SCS Therapy:

For Conventional SCS Therapy, the ENS will be programmed to deliver pulses at a frequency in the 20-200 Hz range with a maximum pulse width of 1 ms. The amplitude of

the electrical signal and the arrays of electrodes used for delivering therapy will be set in order to elicit paresthesia as reported by the patient. Once paresthesia is reported, this will be used to guide the programmer to cover the proper pain dermatome. These parameters and electrode arrangements will be noted and saved in the remote controller. The patient will be educated and trained on operation and troubleshooting the ENS and remote controller.

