Following a satisfactory demonstration on ENS and remote controller operation, the patient will be discharged to home with an emergency 24-hour contact information should the patient have any issues or questions. Programming and training procedure should be approximately 1.5 to 2 hours long. The patient will be scheduled to return to the clinic for the crossover reprogramming visit 4 ± 1 days after the initial programming.

5.5 Clinic Visit 3: Crossover visit:

After 4 ± 1 days of trialing conventional SCS therapy, the patient will return to the clinic for a reassessment of the lead location using x-ray fluoroscopy, and crossover to PM-SCS therapy. Pain level obtained with conventional SCS will be assessed and recorded in CRF05 before crossing over to PM-SCS therapy. The study physician may reposition the leads if deemed necessary upon comparison to the initial x-ray image. If leads have migrated and cannot be re-adjusted, the patient will be exited from the study and subject data will be excluded from the final analysis. After x-ray assessment, stimulation parameters will be programmed as described below for PM-SCS. No therapy will be given for up to one day to allow washout of the conventional SCS therapy.

5.5.1 Polymodal SCS Therapy:

In this case the ENS will be programmed to deliver multiple simultaneous signals with different stimulation parameters to different electrode arrays in the leads. Stimulation signals will be in the 20-1,200 Hz range and a maximum pulse width of 1 ms, which is within the CE Mark and FDA approved parameters. The parameters of each program will be saved in the remote controller. The patient will be educated and trained on operation and troubleshooting the ENS and remote controller as it pertains to PM-SCS therapy.

5.6 Standard of Care Follow up phone visits:

It is standard practice that during a SCS trial period, a Clinical Field Technician (CFT) will contact the patient by phone to track the status of therapy and comfort of the patient.

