6. DATA COLLECTION AND ANALYSIS

6.1 Effectiveness:

A statistical analysis based on analysis of variance will be carried out. Given that this is an early-stage observational study, with a small population size, the analysis may not provide appropriate power and significance of endpoint measurements. Standard statistical analysis including the number of observations, mean, ranges for quantitative variables and relative percent for some categorical variables will be reported as appropriate.

During and at the end of the trial stage, patients will be asked to provide feedback regarding sensations and pain relief as a result of the polymodal stimulation therapy and in comparison with conventional therapy.

Pain intensity will be rated using the numerical pain rate scale (NPRS). Patients will score the severity of pain using this 11-point scale, with zero (0) indicating no pain and ten (10) indicating the worst pain imaginable. The patient will be asked to evaluate the average level of pain experienced during a particular time window between visits. The primary endpoint of record will correspond to the average NPRS score reported at the end of each therapy period. Patients will serve as their own control.

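### The only pre-treatment pain score comes from the eligibility visit, up to 30 days before SCS starts, so each therapy's reduction from baseline probably includes some regression to the mean and any intervening change

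*Combined protocol and SAP*

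**What the plan says.** Section 3.3.1 defines the primary endpoint as "Back pain score reduction relative to baseline pain score (i.e. prior to SCS) at day 5 post-initiation" of each therapy, conventional or polymodal. Section 3.2 sets the objective of showing that stimulation with several simultaneous waveforms relieves pain.

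The entry criterion in 4.1.4 is "Average back pain intensity of ≥ 5 out of 10 on the numerical pain rating scale (NPRS"). Section 5.3 places two things at Clinic Visit 1: "verifying that all inclusion and exclusion criteria are met (using CRF01"), and "baseline pain will be collected and recorded in the appropriate CRFs (CRF02, CRF03, and CRF04").

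Table 2, and the identical schedule in the Protocol Summary, mark Pain NPRS at Enrollment/Baseline (Day 0), at crossover and at end of study. The column between the first two is headed "Start of SCS Trial (0-30 days after enrollment/baseline") and has no NPRS mark. Section 5.4, on Visit 2, describes implantation, programming and training but no pain score. The next score is the one in Section 5.5: "Pain level obtained with conventional SCS will be assessed and recorded in CRF05 before crossing over to PM-SCS therapy".

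On the recall period, Section 6.1 says: "The patient will be asked to evaluate the average level of pain experienced during a particular time window between visits". The same section makes each patient their own comparator. The visible text describes no untreated or sham period, run-in or repeat baseline.

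**The concern.** Two things can enter a reduction measured from such a baseline without being an effect of stimulation.

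1. **Regression to the mean.** If patients are admitted because a noisy score reached 5 and that score is then the reference, later scores will on average be lower even if nothing is done. The direction is known: it favours therapy.
2. **Change before implantation.** The gap may be as long as 30 days, three times the ten-day limit that Section 5.1 puts on the trial period. Any change in pain over that time is counted in the SCS result. It could go either way, or be nil. Pain medication is scheduled for recording at Day 0 only, so a medication change in the gap would not show in the scheduled data.

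With no untreated comparator, the claim that polymodal SCS relieves pain rests on the change from this one score.

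**Working it through.** **Is the gating score the baseline score?** Eligibility is documented on CRF01 and baseline pain on CRF02 to CRF04, so the protocol does not say outright that they are one reading. Both belong to Visit 1, however, and no other pre-treatment NPRS is scheduled. I treat a shared score as a strong inference.

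**Size of regression to the mean.** The plan gives no effect size, SD or sample-size calculation, so there is no figure of its own to reproduce. The only inputs from the documents are the cut of 5 and the 11-point scale (Section 6.1). The rest are assumptions: candidate-pool mean 6.0 to 7.5, SD 1.5 to 2.0, test-retest correlation r 0.5 to 0.8.

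For a normal score selected above a cut, with no treatment effect and no drift:

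expected spurious reduction = (1 − r) × SD × φ(c) / (1 − Φ(c)), where c = (cut − mean) / SD.

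On a whole-number scale, a score of at least 5 corresponds to an underlying value of about 4.5 or more, so the effective cut is 4.5. The result falls with the mean and with r and rises with SD, so the extremes are:

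- Upper end (mean 6, SD 2, r 0.5): c = (4.5 − 6)/2 = −0.75; φ/(1 − Φ) = 0.301/0.773 = 0.389; 0.5 × 2 × 0.389 = **0.39**.
- Lower end (mean 7.5, SD 1.5, r 0.8): c = (4.5 − 7.5)/1.5 = −2; φ/(1 − Φ) = 0.054/0.977 = 0.055; 0.2 × 1.5 × 0.055 = **0.02**.

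Cutting at 5.0 as if the score were continuous would give 0.51 and 0.03 for the same two cases.

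**Check by simulation.** Whole-number scores bounded at 0 and 10 were simulated, with 2,000,000 draws per scenario, no treatment effect and no drift:

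| Pool mean | SD | r | Formula, cut 4.5 | Simulated reduction, conventional | Simulated reduction, PM-SCS |
|---|---|---|---|---|---|
| 6 | 2.0 | 0.5 | 0.39 | 0.40 | 0.40 |
| 6 | 2.0 | 0.7 | 0.23 | 0.25 | 0.25 |
| 7 | 2.0 | 0.7 | 0.12 | 0.13 | 0.13 |
| 7 | 1.5 | 0.7 | 0.05 | 0.05 | 0.05 |

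The spurious reduction is the same under both therapies, and their difference was zero to within simulation error in every scenario. Replacing the gating score with a second, separate pre-treatment reading brought it to 0.00 throughout. As a sensitivity case outside the main range, a pool averaging only 5 (SD 1.5 to 2.0, r 0.5 to 0.9) gave 0.12 to 0.67.

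**Scale.** With n = 25 (the protocol's cap) and an assumed SD of change of 1.5 to 2.5, the 95% half-width for a mean change is 2.064 × SD / √25, or 0.62 to 1.03 points. Regression to the mean is below that throughout the main range, but it is a systematic shift and does not average out.

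**Drift.** The documents give nothing from which to compute it.

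**The case against.** The strongest reply is that the study compares two therapies within patients. A shared baseline drops out of that comparison: (baseline − PM score) − (baseline − conventional score) contains no baseline. This stands. A reader might infer that the polymodal-versus-conventional contrast is biased by the baseline, but for the absolute difference it is not. If reduction were expressed as a percentage, which the protocol does not settle, the baseline would remain as the denominator. The reply does not dispose of the point, because 3.3.1 defines the endpoint as each therapy's reduction from baseline, and the pain-relief objective is read from that.

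Other parts of the opposing case also stand:

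- A reader might take it as stated that the Day 0 score is the qualifying score. The separate CRFs leave that as an inference.
- A reader might conclude that drift flatters therapy. The gap can be 0 days and the direction is unknown. Pain must have been refractory for at least 3 months and medication stable for at least one month, which limits drift at entry.
- A reader might say that the baseline and later recall windows differ. The baseline window is merely unstated in the visible text. The CRFs and appendices are not available, and parts of Section 5.1 are redacted.
- The size rests wholly on assumed inputs and is small if candidates usually score well above 5. A score averaged over a period is also more stable, which corresponds to the higher values of r.
- Section 6.1 already concedes limited power for a small early-stage study. That concerns precision, however, not a shift in one direction.

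**Conclusion.** The point holds for the single-therapy reductions in 3.3.1 and for the objective of showing pain relief. It does not extend to the absolute difference between polymodal and conventional SCS.

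If the Day 0 score is both gate and baseline, each reduction is inflated by about 0.02 to 0.4 NPRS points. This assumes a candidate mean of 6.0 to 7.5, SD 1.5 to 2.0, test-retest correlation 0.5 to 0.8 and an effective cut at 4.5. Any change in pain over a gap of 0 to 30 days is added, with unknown sign and size. The documents do not support saying that drift is present, that it favours therapy, or that the recall windows are mismatched. The likely bias is modest, but it can be reduced at almost no cost.

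**What to change.** - Add Pain NPRS to Table 2 (and the matching schedule in the Protocol Summary) at Clinic Visit 2, before sedation and lead implantation. State its recall window and match it to the later scores as closely as possible.
- Make that score the baseline of record for 3.3.1, and keep the enrolment score for eligibility only.
- Report the number of days from enrolment to Visit 2 and the change in NPRS between them.
- Flag patients whose two visits fall on the same day or whose recall windows overlap. For them the second score is not separate from the gating score and does not remove regression to the mean.

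The cost is one question at a visit that already takes place and one CRF line. The reported reductions may be slightly smaller. The change does not supply an untreated control, so open-label placebo response stays in both reductions.

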5.3 Clinic Visit 1: Enrollment/Baseline Visit

A patient will be enrolled in the study upon signing the ICF, verifying that all inclusion and exclusion criteria are met (using CRF01) and reaffirming voluntary participation, and. Medical history, including pain management, and baseline pain will be collected and recorded in the appropriate CRFs (CRF02, CRF03, and CRF04).

5.4 Clinic Visit 2: Lead Implantation, Conventional SCS Programming and Training Procedure:

Patients will be implanted with commercially available temporary leads as part of the regular SCS trial period and using standard clinical practice. The patient will be placed on a surgical bed in a supine position and may be mildly sedated. The back of the patient will be draped and cleaned using sterile techniques. A properly trained physician will guide and place two percutaneous leads into the epidural space using introducers and steering stylets while under fluoroscopic x-ray guidance. Once the leads are placed above the dorsal aspect of the cord at the proper vertebral level, the introducers and stylets are removed. The exterior portion of the leads will be anchored with sutures or taped firmly to the skin and the proximal ends of the leads connected to an interface cable, which will be plugged into the ENS. The leads and cables will be properly secured to minimize migration of the leads and prevent accidental disconnection. An AP and lateral radiograph of the implanted leads in reference to the vertebral levels will be collected. After the patient has recovered from sedation, programming of conventional SCS therapy will be performed using standard clinical practice.

5.4.1 Conventional SCS Therapy:

For Conventional SCS Therapy, the ENS will be programmed to deliver pulses at a frequency in the 20-200 Hz range with a maximum pulse width of 1 ms. The amplitude of

the electrical signal and the arrays of electrodes used for delivering therapy will be set in order to elicit paresthesia as reported by the patient. Once paresthesia is reported, this will be used to guide the programmer to cover the proper pain dermatome. These parameters and electrode arrangements will be noted and saved in the remote controller. The patient will be educated and trained on operation and troubleshooting the ENS and remote controller.

Following a satisfactory demonstration on ENS and remote controller operation, the patient will be discharged to home with an emergency 24-hour contact information should the patient have any issues or questions. Programming and training procedure should be approximately 1.5 to 2 hours long. The patient will be scheduled to return to the clinic for the crossover reprogramming visit 4 ± 1 days after the initial programming.

5.5 Clinic Visit 3: Crossover visit:

After 4 ± 1 days of trialing conventional SCS therapy, the patient will return to the clinic for a reassessment of the lead location using x-ray fluoroscopy, and crossover to PM-SCS therapy. Pain level obtained with conventional SCS will be assessed and recorded in CRF05 before crossing over to PM-SCS therapy. The study physician may reposition the leads if deemed necessary upon comparison to the initial x-ray image. If leads have migrated and cannot be re-adjusted, the patient will be exited from the study and subject data will be excluded from the final analysis. After x-ray assessment, stimulation parameters will be programmed as described below for PM-SCS. No therapy will be given for up to one day to allow washout of the conventional SCS therapy.

5.5.1 Polymodal SCS Therapy:

In this case the ENS will be programmed to deliver multiple simultaneous signals with different stimulation parameters to different electrode arrays in the leads. Stimulation signals will be in the 20-1,200 Hz range and a maximum pulse width of 1 ms, which is within the CE Mark and FDA approved parameters. The parameters of each program will be saved in the remote controller. The patient will be educated and trained on operation and troubleshooting the ENS and remote controller as it pertains to PM-SCS therapy.

5.6 Standard of Care Follow up phone visits:

It is standard practice that during a SCS trial period, a Clinical Field Technician (CFT) will contact the patient by phone to track the status of therapy and comfort of the patient.

Accordingly, follow up phone visits will be performed as needed during the study. After the first day of therapy and depending on the extent of pain relief reported by the patient, the CFT may instruct the patient to adjust the level of stimulation as deemed appropriate by patient to obtain optimum pain relief. The patient may also be instructed to use a different therapy group in case a therapy cannot be optimized with the previously tried therapy group. This process may be repeated during trial days for both the conventional SCS part of the trial and the PM-SCS part of the trial. Depending on feedback from the phone visits, the PI may decide to schedule a visit to the clinic for reassessing lead position and reprogramming, or to address an adverse event.

5.7 Optional unscheduled clinic visit:

If lead migration is suspected, the PI may schedule a reprogramming visit. In this visit, the PI may evaluate the position of the leads inside the epidural space using x-ray fluoroscopy and reposition and/or reprogram as needed. The PI may also change stimulation parameters using patient feedback as done during the initial visit or during the crossover visit. This visit may also be used to address any other mild or moderate adverse events related to SCS therapy.

5.8 Clinic Visit 4: End of trial period visit:

The patient will return to the clinic as scheduled for an end of trial period visit, in which the stimulation will be stopped, the hardware disconnected from the leads, and the temporary leads removed. Before stimulation is stopped, the patient will be asked to provide feedback about pain status, subjective satisfaction, and paresthesia sensation, which will be recorded in the appropriate CRFs (CRF06, CRF07, and CRF08). This visit may take place any time if the PI deems necessary to exit a patient from the trial and study, or if the patient voluntarily decides to withdraw.

5.9 Other therapies:

As per standard of care practice the patient may continue on prophylactic antibiotics as prevention for bacterial skin infection. Patient will also follow the investigating physician's protocol for anticoagulant therapy, other medications, as well as over-the-counter medications and supplements.

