- 4.2.9** Patients who are undergoing or will undergo therapies or diagnostics that involve electromagnetic fields such as: diathermy based therapies, electrocautery, magnetic resonance imaging (MRI), radiofrequency (RF) or microwave ablation, bone growth stimulators, electrolysis, therapeutic ultrasound, ultrasound, lithotripsy, psychotherapeutic procedures, radiation therapy, and transcutaneous electrical nerve stimulation.
- 4.2.10** A clinically significant disorder such as cerebrovascular disease, pulmonary infarction, ischemic heart disease, cardiac dysrhythmia, myocardial infarction, or congestive heart failure or any other as determined by the investigator
- 4.2.11** Uncontrolled diabetes, uncontrolled pulmonary disease, or uncontrolled hypertension
- 4.2.12** Patients who have evidence of major psychiatric disease, mental disorder, drug dependency, alcohol dependency, or substance abuse disorders
- 4.2.13** Patients who have progressive neurological disease such as multiple sclerosis, chronic inflammatory demyelinating polyneuropathy, rapidly progressive arachnoiditis, acute herniated disc, or any other as determined by investigator
- 4.2.14** Medical condition or pain condition in other body areas that could interfere with study procedures, accurate pain reporting, and/or confound evaluation of study end points
- 4.2.15** Concurrent participation in another clinical study
- 4.2.16** Involvement in an injury claim under current litigation or a pending or approved workers' compensation claim

4.3 Withdrawal:

Subjects may voluntarily withdraw from the study at any time. Withdrawing from the trial will not carry out any sanction and will not affect patient's access to other treatments.

4.4 Terminating Participation:

A patient's participation in the study may be terminated if continued participation in the study is not in the subject's best interest, according to the Principal Investigator's opinion or if the subject withdraws participation from the study. Therapy will be stopped and leads will be removed. Any patient who suffers an adverse event whether or not related to study treatment may withdraw voluntarily from the study.

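### Section 5.5 discards the conventional-SCS pain scores of patients exited at crossover for lead migration, which may overstate mean conventional-SCS relief, probably by a few tenths of a point or less

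*Combined protocol and SAP*

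**What the plan says.** Section 5.5 covers the crossover visit (Visit 3), held after 4 ± 1 days of conventional SCS. Lead position is checked by fluoroscopy and the physician may reposition the leads. If they have migrated and cannot be re-adjusted, "the patient will be exited from the study and subject data will be excluded from the final analysis". The wording covers all of the patient's data, not only polymodal data.

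Two pain scores are planned by that point. At Visit 1 (5.3), "baseline pain will be collected and recorded in the appropriate CRFs (CRF02, CRF03, and CRF04"). At Visit 3 (5.5), "Pain level obtained with conventional SCS will be assessed and recorded in CRF05 before crossing over to PM-SCS therapy". The schedule of events (Table 2) also marks the NPRS at both visits.

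The primary endpoint in 3.3.1 is the reduction from baseline at day 5 "post-initiation of a particular SCS therapy (conventional or polymodal"). Section 6.1 adds: "The primary endpoint of record will correspond to the average NPRS score reported at the end of each therapy period". The same section promises "Standard statistical analysis including the number of observations", but it gives no analysis set and no rule for exited patients.

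Three other places bear on the size:
- Table 1 and 6.3.1 list lead movement at 13.2%, with no time base.
- Section 5.1 caps enrolment at 25 patients and the trial period at ten days.
- Section 5.7 allows an unscheduled visit for suspected migration, at which the investigator may "reposition and/or reprogram as needed".

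**The concern.** Whether a patient stays in the analysis depends on something that happens after conventional stimulation has started. A patient exited at Visit 3 can have a complete result for the conventional-SCS endpoint, baseline and end of period, and the rule deletes it.

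The exclusion may not be neutral. Section 5.4.1 steers conventional SCS by paresthesia over the painful dermatome, and 5.6 lets reported pain relief prompt a reassessment of lead position. The protocol itself therefore links lead position with relief. It is plausible, though not shown, that patients with irreparably displaced leads had less relief. If so, the conventional-SCS mean describes only patients whose leads held or could be corrected, and it is too favourable.

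The stake is limited to that mean. The reader would see a smaller n but not be told in the effectiveness summary why it is smaller. In a study whose stated purpose is feasibility, the number of patients who could not go on to polymodal SCS, and how they fared before exit, is itself of interest.

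**Working it through.** The plan gives no figure for this effect, so there is none to reproduce. The question is how far the conventional-SCS mean could move.

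**Inputs from the documents.** N = 25 (the maximum, 5.1); lead migration 13.2% (Table 1, 6.3.1).

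**Assumptions, not in the documents.** Mean relief is 4 NPRS points in kept patients and *r* = 0 to 2 points in excluded patients. A fraction *f* of migrations cannot be re-adjusted, with *f* = 0.10, 0.25, 0.50 or 1.00.

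**Step 1: by number excluded, using no migration rate.** With *k* exclusions, the mean over all 25 is [(25 − *k*) × 4 + *k* × *r*] / 25, and the reported mean is 4. The difference is

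overstatement = *k* × (4 − *r*) / 25

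| Excluded, *k* | *r* = 2 | *r* = 0 |
|---|---|---|
| 1 | 0.08 | 0.16 |
| 2 | 0.16 | 0.32 |
| 3 | 0.24 | 0.48 |

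As an intermediate case, take three excluded patients with mean relief of 1 point. Then (22 × 4 + 3 × 1) / 25 = 3.64 against a reported 4.00, an overstatement of 0.36. If *r* = 4, the overstatement is 0 for any *k*.

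**Step 2: using the listed rate.** Let *p* = 0.132 × *f*. Expected exclusions are 25*p*, the chance of at least one is 1 − (1 − *p*)^25, and the expected overstatement is *p* × (4 − *r*).

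| *f* | *p* | Expected exclusions | Chance of at least one | Expected overstatement (*r* = 2 to *r* = 0) |
|---|---|---|---|---|
| 0.10 | 0.0132 | 0.33 | 28% | 0.03 to 0.05 |
| 0.25 | 0.033 | 0.825 | 57% | 0.07 to 0.13 |
| 0.50 | 0.066 | 1.65 | 82% | 0.13 to 0.26 |
| 1.00 | 0.132 | 3.3 | 97% | 0.26 to 0.53 |

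The last row is a bound in which every migration is irreparable. It is unlikely, because 5.5 and 5.7 both allow repositioning. The 13.2% may also not apply to a conventional period of 3 to 5 days, which is why Step 1 stands without it.

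**Step 3: against sampling error.** For an assumed SD of 2 to 3 points, the standard error of a mean of 25 is 2/√25 = 0.4 to 3/√25 = 0.6. The shift is mostly below that.

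**Step 4: the paired comparison.** Patients exited at Visit 3 have no polymodal score. They cannot enter a within-patient comparison whether or not the clause exists, so its effect there is zero.

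**Step 5: whether the score exists.** Section 5.5 places CRF05 before crossover but does not say that it precedes the x-ray. The score is due, but not certain to be recorded in every exited patient.

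**The case against.** The strongest case against has four parts.

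- **Little depends on it.** The study is about polymodal SCS, and patients act as their own controls. The paired comparison and the polymodal mean are untouched. If anything, an overstated conventional mean favours the comparator.
- **The rule is defensible.** It is set in advance, rests on lead position rather than on the pain score, and applies before any polymodal data exist. Analysing only patients who can enter both periods is a recognised choice.
- **The gap is assumed and may be smaller.** The NPRS is an average over the interval between visits, so a late migration affects it only partly. Phone contact and unscheduled visits may already have corrected early losses of relief. With *f* at 0.10 or 0.25 the chance of no exclusion at all is 72% or 43%, and the shift lies within sampling error.
- **The cure has its own risk.** Returning these patients to the conventional mean alone means that the two period means rest on different patients. With *k* = 3 and *r* = 0, the conventional mean falls from 4.00 to 3.52 while the polymodal mean stays put. Set side by side, they differ by a further 0.48 points in favour of polymodal SCS.

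Much of this stands. The effect is small, its direction is conditional, and migration is still reported as an adverse event under 6.3, so its occurrence can be traced. What does not follow is that the clause is needed. Restricting the paired comparison to patients with both scores requires no deletion of conventional-period results, and 3.3.1 makes those results part of the primary endpoint. The last objection is met by basing the comparison only on the paired set and stating n for each analysis.

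**Conclusion.** The concern holds. Followed as written, 5.5 removes evaluable primary-endpoint data from the conventional-SCS summary because of a post-treatment event, and no other section restores them. If the excluded patients had less relief, the conventional mean is overstated by 0.08 to 0.16 points per excluded patient, and probably by a few tenths or less in total. About half a point needs roughly three exclusions with no relief at all. These sizes rest on the assumed relief values and, for the rate-based figures, on the assumed irreparable fraction and on 13.2% applying to this short period. That the data are excluded is certain from the text; that a bias results is plausible but not established. The point does not reach the paired comparison or the safety reporting. It should be fixed because the remedy is simple and the loss avoidable.

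**What to change.** In 5.5, delete the part of the sentence that removes the patient's data from the final analysis. The decision to exit the patient is unchanged.

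In 6.1, add wording such as: *All patients who started conventional SCS and have both a baseline and a conventional-period (CRF05) NPRS score are included in the conventional-period summary, including those exited for lead migration. The paired comparison uses only patients with scores in both periods. The number exited at crossover for lead migration and the number without a CRF05 score are reported, and n is stated for each analysis.*

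No sensitivity analysis assigning polymodal outcomes to exited patients is needed.

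The cost is wording in two sections, with no new visits, data or patients. The conventional-SCS mean may become slightly less favourable, and n will differ between the conventional-period summary and the paired comparison. For that reason the report should draw any contrast between therapies from the paired set, not from the two separate means.
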